9.2.1.1. Suspected Unexpected Serious Adverse Reactions

Suspected unexpected serious adverse reactions (SUSARs) are serious events that are not listed in the IB, and that the investigator identifies as related to investigational product or procedure. United States 21 CFR 312.32 and European Union Clinical Trial Directive 2001/20/EC and the associated detailed guidances or national regulatory requirements in participating countries require the reporting of SUSARs. Lilly has procedures that will be followed for the recording and expedited reporting of SUSARs that are consistent with global regulations and the associated detailed guidances.

9.2.1.2. Adverse Event Monitoring with a Systematic Questionnaire

The C-SSRS (Posner et al. 2011) captures the occurrence, severity, and frequency of suicide-related thoughts and behaviors during the assessment period. The scale includes suggested questions to solicit the type of information needed to determine if a suicide-related thought or behavior occurred. The tool was developed by the Columbia Group (Posner et al. 2011) to prospectively categorize suicide-related events.

Before administering the C-SSRS, study site personnel will question the patient about any change in the preexisting condition(s), and the occurrence and nature of any AEs.

Nonserious AEs obtained through the questionnaire are recorded and analyzed separately. Only SAEs and AEs leading to discontinuation, elicited through the C-SSRS are to be recorded as AEs via eCRF. Serious adverse events must be reported to Lilly or its designee within 24 hours as

SAEs. Any suicidal behavior, or suicidal ideation per Items 4 or 5 (Active Suicidal Ideation with Some Intent to Act, Either without Specific Plan or with Specific Plan and Intent) would prompt referral of the patient to a mental health professional.

9.2.2. Complaint Handling

Lilly collects product complaints on investigational products and drug delivery systems used in clinical studies in order to ensure the safety of study participants, monitor quality, and to facilitate process and product improvements.

Patients will be instructed to contact the investigator as soon as possible if he/she has a complaint or problem with the investigational product (or drug delivery system, such as a prefilled syringe), so that the situation can be assessed.

9.3. Treatment of Overdose

No data are available at this stage of development.

9.4. Safety

9.4.1. Electrocardiograms

For each patient, a single, 12-lead digital ECG will be collected according to the Schedule of Activities (Section 2). Electrocardiograms will have a central overread, except for screening, and should be recorded according to the study-specific recommendations included in the ECG manual.

Any clinically significant finding from ECGs that results in a diagnosis should be reported to Lilly or its designee as an AE via eCRF.

9.4.2. Vital Signs and Weight

Vital signs will include body temperature, blood pressure, and pulse. Blood pressure and pulse will be measured, in triplicate, in the sitting position prior to blood draws and study drug administration (see Schedule of Activities [Section 2]). Weight will be measured at screening and at Visits 12 and 14 or at ET (see Schedule of Activities [Section 2]).

Any clinically significant finding from vital signs measurement that results in a diagnosis should be reported to Lilly or its designee as an AE via eCRF.

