Study Period (SP)	SP I- Screening	SP II- Prospective Baseline	SP III – Treatment										SP IV – Follow-up	
			30-45	14	16	30	30	30	15	15	15	15	60	60
(Target) Interval (days) since previous visit														
Allowable range (days) between visits	3-45	30-40 ^a												
Interval allowance (days) compared from previous visit				± 1	± 3	± 2	± 2	± 2	± 2	± 2	± 2	± 2	± 5	± 5
Visit	1	2	3	4 ^b	5	6	7	8	9 ^c	10	11 ^c	12/ET	13	14/ET
Month			0	0.5	1	2	3	4	4.5	5	5.5	6	8	10
PSMQ-M					X							X		
HCRU and Employment status			X		X	X	X	X		X		X	X	X
C-SSRS/SHSF, SHFU ^f	X	X	X		X	X	X	X		X		X	X	X

Abbreviations: AE = adverse event; CGRP = Calcitonin-gene related peptide; CRP = Lilly Clinical Research Physician; CRS = Lilly Clinical Research Scientist; C-SSRS = Columbia Suicide Severity Rating Scale; DNA = deoxyribonucleic acid; ECG = electrocardiogram; ePRO = electronic patient-reported outcomes; ET = early termination; FSH = follicle stimulating hormone; HbA1c = glycated hemoglobin; HCRU = Health Care Resource Utilization; MIDAS = Migraine Disability Assessment test; MSQ (v2.1) = Migraine Specific Quality of Life Questionnaire; PGI-I = Patient Global Impression of Improvement; PGI-S = Patient Global Impression of Severity; PK = pharmacokinetics; PSMQ-M = Patient Satisfaction with Medication Questionnaire-Modified; RNA = ribonucleic acid; SP = Study Period; SHSF = Self-harm supplement form; SHFU = Self-harm follow-up form.

Note: Selected tests may be obtained in the event of a treatment-emergent hepatic abnormality, and follow-up may be required with patients, in consultation with the Lilly, or its designee (CRP/CRS). See [Appendix 4](#) for more details regarding specific hepatic monitoring tests. If the patient has discontinued the trial and returns for hepatic follow-up, the site should use the 800 series as the visit designation.

- ^a The eligibility period of the prospective baseline assessment will last from 30 to 40 days. Investigators and patients may have up to an additional 5 days to schedule their Visit 3 appointment (beyond the 40 days); however, eligibility will be based on the 30-40 day period.
- ^b Visit is to include a review of any spontaneously reported AE, concomitant medications and collection of blood samples for immunogenicity, PK, and CGRP plasma.
- ^c Visit is to include a review of any spontaneously reported AE, concomitant medications and collection of blood samples for PK, and CGRP plasma.

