5.1. Overall Design

Study CGAN is a multisite, randomized, double-blind, placebo-controlled bridging study of galcanezumab in Japanese outpatients suffering from migraine. The study has 4 periods, including a prospective baseline phase to determine patient eligibility. Patients who complete Study Period III may have an option to roll-over to the open-label extension study, I5Q-JE-CGAP (CGAP). [Figure CGAN.5.1](#) illustrates the study design.

^aEligibility period determined between a minimum of 30 days and a maximum of 40 days. Investigators may have up to 5 additional days (beyond the 40 days) if needed to schedule patients' Visit 3 appointment.

^aPatients randomized to the 120 mg dose will receive a loading dose of 240 mg at the first injection only (Visit 3).

Approximately 240 enrolled patients roll-over to I5Q-JE-CGAP study (Open Label Extension) at visit 12

Abbreviations: SP = study period.

Figure CGAN.5.1. Illustration of study design for Study I5Q-JE-CGAN.

Study Period I: The study and potential risks for both study I5Q-JE-CGAN and I5Q-JE-CGAP will be explained to the patient at Visit 1. The informed consent form (ICF) must be signed before any study procedures are performed. Patients are required to discontinue all excluded medications or migraine-prevention treatments at least 30 days prior to Visit 2. Botulinum toxin A or B in the head or neck area must be discontinued at least 4 months prior to Visit 2.

The screening visit (Visit 1) will consist of a full clinical assessment, including a comprehensive medical evaluation documenting medical history, and a physical and neurological examination (Section 2). Visit 1 will be complete when the last scheduled procedure of the screening assessment is completed.

Study Period II: Qualified patients will enter Study Period II (prospective baseline) to determine their eligibility for the study, and to establish baseline data for comparison of endpoints during the treatment period. Beginning at Visit 2, patients will log in daily to the electronic patient-reported outcomes (ePRO) system to answer questions about the occurrence of headaches, headache duration, headache features, severity of headache, and use of headache medication. At the end of the prospective baseline period, sites will be notified whether their patients met the criteria and are eligible to be randomized to treatment at Visit 3.

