## LY2951742 (Galcanezumab)

I5Q-JE-CGAN is a multisite, randomized, double-blind, placebo-controlled, bridging study of galcanezumab in Japanese outpatients suffering from episodic migraine. The study is comprised of 4 periods: 1) Screening (3-45 days), 2) Baseline for assessment of the type, frequency and severity of headaches (30-40 days), 3) Double-blind treatment phase (6 months), and 4) Follow-up (4 months). Patients who complete Study Period III may have an option to roll-over to the open-label extension study, I5Q-JE-CGAP. Patients will be randomized 2:1:1 to either placebo, 120 mg, or 240 mg LY2951742 administered as a subcutaneous (SC) injection once every month.

Eli Lilly Japan K.K. Kobe, Hyogo, Japan  
I5Q-JE-CGAN

Statistical Analysis Plan electronically signed and approved by Lilly on date provided below.

Approval Date: 15-Nov-2018 GMT

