Study Period / Analysis	Patient Population	Baseline Observation	Post-baseline Observation(s)
and ECGs	post-baseline observation	Minimum value from Visits 1–3  High: Maximum value from Visits 1–3	Minimum value from Visits 3.01–12  High: Maximum value from Visits 3.01–12
Continuous safety analyses (Repeated Measures)	Safety Population with a baseline and at least one post-baseline observation	Last of Visits 1–3	Scheduled visits: 3 < Visits <= 12
Continuous safety analyses – change from baseline to LOCF endpoint (ANCOVA)	Safety Population with a baseline and at least one post-baseline observation	Last of Visits 1–3	Last scheduled visit: 3 < Visit <= 12
Study Period III and IV combined			
Primary / Key Secondary efficacy analyses	ITT Population with a baseline and at least one post-baseline observation	Visit 3	All Visits 3.01–14
Quality of Life analyses	ITT Population with a baseline and at least one post-baseline observation	Visit 3	All Visits 3.01–14
Continuous safety analyses (Repeated Measures)	Safety Population with a baseline and at least one post-baseline observation	Last of Visits 1–3	All Visits 3.01–14
Treatment emergent immunogenicity	Safety Population, ADA follow-up cohort (See Section 5.5.12.1.6)	Visit 3	All Visits 3.01–14
Study Period IV			
Continuous safety analyses – change from baseline to LOCF endpoint (ANCOVA)	Post-treatment Population with a baseline and at least one post-baseline observation	Last of Visits 1–12	Last Visit: 12.01–14
FEAEs	Post-treatment Population	All Visits 1–12. Pre-existing condition that is still ongoing at Visit 1 should be evaluated as baseline values.	All Visits 12.01–14
Serious Adverse Events, Discontinuations due to Adverse Events	Post-treatment Population	NA	All Visits 12.01–14
Follow-up emergent abnormal laboratory values	Post-treatment Population with normal laboratory values at all nonmissing baseline visits (with	All Visits 1–12	All Visits 12.01–14

Study Period / Analysis	Patient Population	Baseline Observation	Post-baseline Observation(s)
	respect to direction being analyzed) and who have at least one post-baseline observation		
Follow-up emergent changes in vital signs, weight and ECGs	Post-treatment Population with a baseline and at least one post-baseline observation	Low: Minimum value from Visits 1–12  High: Maximum value from Visits 1–12	Low: Minimum value from Visits 12.01–14  High: Maximum value from Visits 12.01–14

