#### **5.5.4. Patient Characteristics**

The following patient characteristics at baseline will be summarized by treatment group for ITT patients.

- Demographic (age, gender, race and subrace, height, weight, body mass index, Age [ $<20$ ,  $\geq 20$ ])

Note: body weight (as well as BMI) is based on the last observation before Visit 3 injection.

- Baseline MHD category per 30 day ( $<8$ ,  $\geq 8$ ) (Visit 2 to Visit 3) (by ePRO)
- Years since migraine diagnosis
- Migraine and headache related measures (e.g. number of non-MHD with aura, number of migraine headache days with Criteria C), and acute treatment related measures (e.g. number of MHD with triptans use, number of days with triptan use) per 30-day baseline period (Visit 2 to Visit 3) used for secondary and other efficacy measures as listed in
- PGI-S,
- MIDAS (total, each question)
- MSQ (total, 3 sub scores)
- Previous migraine prevention treatment (Yes, No, Yes and did not fail, Yes and fail  $\geq 1$ , Yes and fail  $\geq 2$ ) (Visit 1)
- Number of previous migraine prevention treatment fail (Visit 1)
- Past usage (yes/no) or current usage (yes/no) of followings: Alcohol, caffeine, nicotine replacement therapy, and tobacco and nicotine combined

Note: Except caffeine, summaries are based on patients with  $\geq 20$  years old.

- Medical history (except primary medical conditions). Medical history is defined as illness(es) that ended prior to the signing of informed consent. It will be summarized by preferred term (PT).
- Pre-existing condition (Visit 1). Pre-existing conditions are those AEs existing at Visit 1. It will be summarized by preferred term (PT).
- Number of Comorbid conditions other than migraine. Comorbid conditions other than migraine are those AEs existing before Visit 3 and continuing after Visit 3 other than migraine. (i.e., not contained “migraine” as PT). If it ends on Visit 3, then it is not a comorbid condition. The count is based on PT. (2 events with different LLT but the same PT will be counted as one comorbid condition.)
- Some other baseline variables used for the subgroup analysis in [Table CGAN. 5.8:](#)
  - Having aura or not at baseline (Yes/No) (Visit 2 to Visit 3)
  - Baseline ADA status (Yes/No) (Visit 3)
  - Baseline body weight (weight  $\leq$  median, median  $<$  weight).

Baseline MHD difference by IWRS and ePRO eligibility day will be summarized. Its listing will be created.

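### No weight is scheduled at Visit 3, so the weight baseline is the screening value 33 to 90 days before first dose and pre-dose change counts as treatment-emergent

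*Protocol*

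**What the plan says.** **Schedule.** Protocol 9.4.2: "Weight will be measured at screening and at Visits 12 and 14 or at ET". The Weight row of the Schedule of Activities (Protocol Section 2) matches: Visits 1, 12 and 14, or early termination. In the same table, vital signs, ECG, hematology and clinical chemistry all have an entry at Visit 3.

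**Baseline.** SAP Table CGAN. 5.4 gives treatment-emergent vital signs, weight and ECGs one common rule. For a decrease the baseline is "Minimum value from Visits 1–3"; for an increase it is the maximum over the same visits, compared with "Maximum value from Visits 3.01–12". Continuous safety analyses use the last value from Visits 1 to 3. For patient characteristics, SAP 5.5.4 says that "body weight (as well as BMI) is based on the last observation before Visit 3 injection", and the body-weight subgroup in Table CGAN. 5.8 uses the same rule.

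**Criteria and analyses.** Table CGAN. 5.6 classes a weight gain or loss of at least 7% as treatment-emergent, and the arms are compared by Fisher's exact test. SAP 5.5.12.2 analyses change in weight during Study Period III by ANCOVA to the LOCF endpoint.

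**Washout.** Protocol 5.1: "Patients are required to discontinue all excluded medications or migraine-prevention treatments at least 30 days prior to Visit 2". Also: "Botulinum toxin A or B in the head or neck area must be discontinued at least 4 months prior to Visit 2".

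**The concern.** A baseline for an on-treatment safety measure should sit close to the first dose. Here the only scheduled pre-dose weight is taken at screening, and the only scheduled weight in the treatment phase is at Visit 12 or early termination. Nothing scheduled in between can separate change before dosing from change on treatment. The SAP's patient-characteristics rule reads as if a value near the injection will exist, but the schedule does not supply one. Vital signs, ECGs and laboratory tests do not have this gap.

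Two things are at stake for weight, which is a listed safety parameter. The proportion of patients with a change of 7% or more, read as a treatment-period figure, may be too high in every arm. Extra variation unrelated to treatment may also make a drug effect on weight harder to see.

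**Working it through.** **Inputs**
- Visit 1 to Visit 2: 3 to 45 days (Schedule of Activities; SAP study summary).
- Visit 2 to Visit 3: 30 to 40 days, plus up to 5 days for scheduling (Schedule of Activities, footnote a).
- Visit 3 to Visit 12: the target intervals sum to 14+16+30+30+30+15+15+15+15 = 180 days.

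**Reproducing the plan's figures.** 30 to 40 days plus up to 5 gives the 30 to 45 days shown as the Visit 3 target interval. 180 days is 6 months of 30 days, as the SAP defines a month.

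**Gap from baseline weight to first dose**
- Minimum: 3 + 30 = 33 days.
- Maximum: 45 + 40 + 5 = 90 days (85 without the scheduling days).

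**Pre-dose share of the Visit 1 to Visit 12 interval**, gap/(gap + 180)
- 33/213 = 15%.
- 90/270 = 33%.

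**Where washout falls.** The stop date is tied to Visit 2, not Visit 1.
- If screening lasts under 30 days, a preventive must already have been stopped before Visit 1: for a 3-day screening, at least 30 − 3 = 27 days before.
- A patient still on a preventive at Visit 1 needs at least 30 days to Visit 2. The gap to first dose is then 30 + 30 = 60 to 45 + 45 = 90 days.
- For botulinum toxin, taking 4 months as about 120 days, the stop is at least 120 − 45 = 75 days before Visit 1.
- Patients on no preventive have no washout.

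**Effect on precision.** The documents give no model for weight variation, so two assumed cases bracket it.
- Weight fluctuates around a stable level: the variance of a change does not depend on the interval, so the ratio is 1 and the increase is about 0%.
- Variance grows linearly with time, with no measurement error: 213/180 = 1.18 at 33 days and 270/180 = 1.50 at 90 days. Standard errors scale as √1.18 = 1.09 and √1.50 = 1.22, so they are 9% to 22% wider.

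**Effect on the 7% incidence, linear-growth case only.** Assume a zero-mean normal change whose 180-day SD is s (percent of body weight). With a gap of g days, S = s·√((180 + g)/180), and the share with a change of at least 7% in either direction is 2·(1 − Φ(7/S)).

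| Assumed s | Visit 3 baseline | 33-day gap | 90-day gap |
|---|---|---|---|
| 2.5% | 0.5% | 1.0% | 2.2% |
| 3% | 2.0% | 3.2% | 5.7% |
| 4% | 8.0% | 10.8% | 15.3% |

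Under the stable-level case the three columns would be equal.

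**The case against.** The strongest reply is that weight is judged against concurrent placebo. Patients are randomized at Visit 3, after the Visit 1 weight and after any washout, so pre-dose change is balanced across arms in expectation. That stands. A reader might infer that the drug-placebo comparison of weight is biased; the design does not support that.

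A reader might also infer that the baseline weight always precedes the preventive washout. It does not. The washout follows it only for patients who stop a preventive after Visit 1, and the documents do not say how many there will be.

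Third, the 18% to 50% variance figure rests on one assumed model, and its upper end needs every patient at the limit of all the windows. If weight is stable apart from fluctuation, the loss is near zero. This also stands, so the range has to start at about 0%.

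Fourth, the baseline rule is prespecified and is shared with vital signs and ECGs for the categorical criteria. Unscheduled values count in categorical safety analyses (SAP 5.5.12.1), so an unscheduled pre-dose weight would be used. This is true, but nothing in the plan asks for such a weight. For vital signs and ECGs the same rule does draw on a Visit 3 value.

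Finally, weight is one item in a list of safety parameters and is neither a primary nor a key secondary endpoint. That limits the priority. It does not remove the point.

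**Conclusion.** The point holds as a small weakness in the assessment schedule. On scheduled data the weight baseline is the Visit 1 value, 33 to 90 days before first dose; for patients who stop a preventive after Visit 1 the gap is 60 to 90 days and includes the washout. Change over that time enters the treatment-emergent figures.

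The consequence is possible added noise and possible inflation of the absolute 7% incidence in every arm. The day counts and the 15% to 33% share follow from the visit windows and a nominal 180-day treatment phase. The statistical cost is by assumption only and runs from none to the linear-growth values above. Priority is minor.

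**What to change.** Add a pre-dose weight at Visit 3 to the Schedule of Activities and to Protocol 9.4.2.

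Table CGAN. 5.4 need not be rewritten. The last-value rule for Visits 1 to 3 and the rule in SAP 5.5.4 would use the new value for the continuous, baseline and subgroup analyses. The minimum/maximum rule can stay for the 7% criteria, in line with vital signs and ECGs. With a Visit 3 weight in the window, a pre-dose gain raises the maximum and a pre-dose loss lowers the minimum, so neither would be counted as treatment-emergent in its own direction.

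The cost is one extra weighing per patient at a visit where vital signs are already taken, plus a short protocol change. If it is too late to change the schedule, state the limitation in the SAP and the clinical study report, and tabulate the interval from baseline weight to first dose by arm.

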9.4.3. Laboratory Tests

For each patient, laboratory tests detailed in (Appendix 2) should be conducted according to the Schedule of Activities (Section 2).

Any clinically significant finding from laboratory tests that results in a diagnosis should be reported to Lilly or its designee as an AE via eCRF.

In addition, an immunogenicity and PK serum sample will be collected, when possible, for any patient who experiences a potential systemic allergic/hypersensitivity reaction during the study,

as judged by the investigator. This immunogenicity and PK serum sample should be collected immediately or as soon as possible, taking into consideration the availability and well-being of the patient. In this case, serum concentrations of galcanezumab will be determined for immunogenicity evaluation. Exact date and time of the sample should be recorded on the laboratory requisition form.

9.4.4. Safety Monitoring

Lilly will periodically review evolving aggregate safety data within the study by appropriate methods.

Investigators are responsible for monitoring individual patient safety throughout the trial. If a study patient/subject experiences elevated ALT $\geq 3X$ ULN, ALP $\geq 2X$ ULN, or elevated TBL $\geq 2X$ ULN, clinical and laboratory monitoring should be initiated by the investigator. Details for hepatic monitoring depend upon the severity and persistence of observed laboratory test abnormalities. To ensure patient/subject safety and to comply with regulatory guidance, the investigator is to consult with the Lilly CRP/CRS regarding collection of specific recommended clinical information and follow-up laboratory tests (see [Appendix 4](#)).

9.5. Pharmacokinetics

At the visits and times specified in the Schedule of Activities (Section 2), venous blood samples of approximately 2.5 mL each will be collected to determine the serum concentrations of galcanezumab.

A maximum of 3 samples may be collected at additional time points during the study, if warranted and agreed upon between both the investigator and sponsor. Instructions for the collection and handling of blood samples will be provided by the sponsor.

When a blood sample is collected, the time and date of last-dose administration prior to blood sampling should be recorded. The actual date and time (24-hour clock time) of each sampling will be recorded. Galcanezumab concentration information that may/would unblind the study will not be reported to investigative sites or blinded personnel until the study has been unblinded. Bioanalytical samples collected to measure investigational product concentration will be retained for a maximum of 1 year following last patient visit for the study.

A validated assay will be used to determine serum galcanezumab concentrations. Samples will be analyzed at a laboratory approved by the sponsor. It is intended that blood samples collected from patients who received placebo should not be analyzed for determination of serum concentrations of galcanezumab.

